### **6.5. Unanticipated Adverse Device Effect (UADE)**

An UADE is defined as "any serious adverse effect on health or safety or any life-threatening problem or death caused by, or associated with, a device, if that effect, problem, or death was not previously identified in nature, severity, or degree of incidence in the investigational plan or application, or any other unanticipated serious problem associated with a device that related to the rights, safety, or welfare of subject." AEs that might reasonably occur because of placement or attempted placement of the investigational product or during follow-up were identified through a risk analysis. The Risk Analysis lists clinical risks to the subject associated with study participation.

If Paradigm Spine determines that UADE of an investigational device presents an unreasonable risk to study subjects, Paradigm Spine/physician will:

- terminate the investigation, or the parts of the investigation presenting that risk, within 5 working days after Paradigm Spine makes an "unreasonable risk" determination or within 15 working days after Paradigm Spine first received notice of the UADE,
- immediately investigate and evaluate the adverse effect (21 C.F.R. § 812.46(b)(1) and (2)),
- report the results of the investigation to all reviewing IRBs and to all participating investigators within 10 working days after Paradigm Spine first receives notice of the UADE (21 C.F.R. § 812.150(b)(1)),
- resume the study, if appropriate, as specified by the IRB.
- notify FDA of event and any action taken by Paradigm Spine as a result of this UADE.

### **6.6. Event Reporting:**

The FDA's Medical Device Reporting requirements regulations state the following requirements for event reporting:

MDR Mandatory Reporting Requirements:

**Manufacturers:** are required to report to FDA when they learn one of their devices may have caused or contributed to a death or serious injury. Manufacturers must also report to FDA when they become aware that one of their devices has malfunctioned and would be likely to cause or contribute to a death or serious injury if the malfunction happened again. Deaths, serious injuries and malfunctions must be reported to FDA within 30 calendar days from the manufacturer becoming aware of an event. Use FDA form 3500A.

Events that require remedial action to prevent an unreasonable risk of substantial harm to the public health and other types of events within 5 work days from becoming aware of an event. Use FDA Form 3500A.

**User Facilities:** User Facilities (e.g., hospitals, nursing homes) are required to report a suspected medical device-related death to both the FDA and the manufacturer. User facilities should report a medical device-related serious injury only to the manufacturer. If the medical device manufacturer is unknown, the user facility should report the serious injury to FDA. A user facility is not required by the MDR regulation to report a malfunction, but can use the voluntary MedWatch program to advise FDA of problems with medical devices. Health-care professionals within a user-facility should familiarize themselves with their institution's procedures for reporting adverse events to the FDA. See "Medical Device Reporting for User Facilities", a guidance document issued by FDA.

**In this trial all SAEs reported by the investigators will be evaluated but only MDRs will be reported to the FDA by the sponsor.**

## 6.7. Documentation of Adverse Events

New or worsening AEs will only be documented for each patient until the last study related patient visit.

The investigator will assess and record any AE in detail on the 'AE' form included in the case report forms (eCRFs).

Investigators will actively check for and report potential device- or procedure- related Adverse Events for all study patients in the time period between the first device application and the end of the clinical phase of the trial at the site.

Investigators will also report to the CRA all unexpected (i.e., not listed in Section 6.1) and Serious Adverse Events (see Section 6.4 for contact information) by completing the Adverse Event eCRF in the EDC. The CRA will forward this report to the sponsor. The sponsor will then make an evaluation if he agrees that the unexpected and serious AE was in fact device- or procedure-related. It is the reporting responsibility of the Investigator to notify the responsible IRB of Adverse Events which are classified by the sponsor as serious, unexpected and related, unless otherwise required and documented by the IRB.

All AEs must be recorded and followed up until the event is either resolved or adequately explained, even after the patient has completed the clinical investigation.

## 7. Statistical Analysis

### 7.1. Accounting for Non-Randomized Treatment Group Comparisons

This study design includes concurrently enrolled, but non-randomized investigational and control arms. Covariate balance will be achieved using sub classification based on propensity score (PS) quintiles. The PS subclasses will be determined by an outcomes-blinded statistician soon after prospective enrollment is completed and before most if not all patients are evaluable for the two-year effectiveness endpoint. The process of assigning patients to subclasses will be submitted to FDA for review and acceptance prior to unblinding of the PS statistician. Selection into a PS subclass is the observational study equivalent to randomization. Subclasses will be determined using methods summarized below to ensure that within subclass, groups are well balanced for a rich set of clinically relevant baseline covariates. Analyses will proceed as if patients were

randomized to treatment group within subclass and effectiveness outcomes will be compared between groups using methods that account for PS subclass. There is a compelling case to be made that informative prior Bayesian designs are especially appropriate for post approval studies (PAS) since recent rigorous objective data is available. To make use of this prior information, a Bayesian design with informative priors has been specified for each Objective. For these Objectives, patient-level data from the IDE study are used to formulate the PAS prior distributions.

To make use of the beta-binomial updating from prior to posterior it is necessary to have counts of the numbers of successes and failures observed among the prospectively enrolled patients for both groups. These counts are added to prior beta distribution parameters that reflect (what amounts to) the prior numbers of success and failures. Combined, these sums of successes and failures determine the Bayesian posterior distribution. The simplicity of this approach stems from the mathematical convenience of conjugate priors which have, in addition to computational convenience, the practical advantage of being interpreted as additional data (Gelman, 2014). However, the numbers of successes and failures observed from each group to be used to update the prior distribution must account for the propensity subclass design.

The following approach will be used to determine adjusted numbers of successes and failures that account for the relative contribution of each PS subclass. This approach is necessary to produce results that take advantage of the covariate balance achieved through PS sub classification. We first consider how this would be done if there was no missing data. This is the approach that will be used in sensitivity analyses involving the several completers analysis sets defined primarily across time. The section below concerning missing data shows how missing data will be incorporated in the primary determination of the Bayesian probability of superiority and non-inferiority.

To adjust for PS subclass, the average success rate over the 5 subclasses will be computed for each treatment group. This is to allow each quintile subclass to contribute equally to the estimated success rates. Consequently, the covariate balance is preserved in the final estimates of CCS probabilities. By equally weighting the PS subclasses, the results become estimates of expected values under the assumption of randomized treatment assignment within PS subclass. Under this assumption, we would expect approximately the same number of investigational and control patients within each subclass implying the equality of weights. The PS adjusted failure probability for each group will be computed as one minus the adjusted success probability.

If the crude numbers of success and failures were used to update the priors, imbalance in the numbers of investigational and control subjects within subclasses would clearly result in a biased treatment effect estimate whenever overall success rates differed among PS subclasses.

By combining the subclass success probabilities in this way, the weights given to each subclass contribution when determining the total numbers of successes and failures used to update the prior are the same for both groups.

The PS subclass adjusted success and failure probabilities will be multiplied by the total treatment group specific sample sizes (across all subclasses) to determine PS subclass adjusted numbers of successes and failures for each group. The adjusted numbers of success and failures in each group will be added to the group specific beta distribution parameters to update the prior

---

 Gelman, A. (2014). *Bayesian data analysis* (Third edition. ed.). Boca Raton: CRC Press.

distributions and determine the posterior distribution of the group differences in success probability.

The theoretical justification for this approach arises from causal analysis concepts. In causal analyses that use propensity score subclassification, Average Treatment Effect (ATE) is determined as the within subclass total sample size weighted average of subclass specific effect sizes. The proposed strategy is consistent with how ATE estimates of relative effectiveness are determined.

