**Ho:  $CCS_{PAS} \leq 0.662 - 0.10 = -0.562$  (inferior)**

**Ha:  $CCS_{PAS} > 0.662 - 0.10 = -0.562$  (not inferior).**

**Non-inferiority will be concluded if the posterior probability is at least equal to 0.95.**

If the inferiority hypothesis is rejected, then the numbers of coflex® successes and failures observed in the PAS will be used to update the Bayesian posterior probabilities of non-inferiority and superiority relative to fusion that were first established in the IDE study and reported in the coflex® SSED. This will facilitate a formal accumulation and summary of what has been learned about the relative effectiveness of coflex® compared to fusion based on pooling relevant information from the IDE trial and this PAS. As reported in the coflex® SSED, the Bayesian posterior probability that coflex® is not clinically inferior to fusion ( $\delta=-0.10$ ) is 0.999362. Similarly, the Bayesian posterior probability that coflex® is superior to fusion in terms of Month 24 CCS was reported to be equal to 0.927550.

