### 7.7.2. Objective 2: 2-Year Non-Inferiority

Bayesian simulations were performed to evaluate the operating characteristics for testing the Objective 2 non-inferiority hypothesis. In the pivotal IDE study, 135 of 204 patients (66.2%) achieved Month 24 CCS. These results were used to define the prior distribution for coflex® in conjunction with surgical decompression as beta (135.5, 69.5) since the distribution prior to the IDE trial was specified as beta (0.5, 0.5). This Jeffries non-informative prior was assumed for patients undergoing decompression alone. A non-inferiority margin of -0.10 is specified. Non-inferiority will be concluded if the Bayesian posterior probability that ( $CCS_{coflex+decomp.} - CCS_{decomp.} > -0.10$ ) is at least equal to 0.95. When evaluating statistical power, it was assumed that the true success rate 0.662 for patients treated with coflex®. However, preliminary results from the German decompression study suggest some an advantage of coflex® over decompression alone. Therefore, when evaluating power, Month 24 CCS for decompression alone was assumed to be at least 2% lower, or 0.642. In contrast, Type 1 error was evaluated by assuming that the coflex® success rate 0.662 but that the success rate for decompression was 0.10 larger. With N=150 patients per group, power was shown to be 89%; and type 1 error was shown to be 0.042 and 0.052 'prior to the prior' and with the prior engaged, respectively.

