#### **7.7.4. Objective 4: Real Conditions of Use**

Non-informative priors were assumed for the both comparisons groups, since IDE results cannot be used as the basis of an informative prior if the comparison is to be made to that same IDE trial. However, the Bayesian simulation R function was modified to reflect that it is known that exactly 135 successes were observed among 204 evaluable patients in the coflex IDE analysis set (see Simulation Report, Section 8.3). Otherwise, all other features of the Bayesian simulation were kept the same.

A design was identified that uses a non-inferiority margin of -0.1175 and a 0.95 posterior probability threshold. This design has an estimated type 1 error of 0.045 and power of about 80%. Other assumptions include expected success rates 0.662 in both groups when determining power and assuming that the Month 24 success rate in the PAS population is 0.10 smaller than in the IDE study population for evaluating type 1 error.

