## 7.11. Handling of Missing Data for Primary CCS Endpoints

### 7.11.1. Bayesian Multiple Imputation

To best preserve an intent-to-treat analysis, the testing of the primary Month 60 superiority hypothesis (Objective 1) will be done on the ITT-PS selected analysis set. Those subjects who withdraw, or who are lost to follow-up (LT FU) after enrollment will be included in the analysis using a modification of Bayesian multiple imputation to accommodate the PS subclass design. This analysis will be the primary analysis, but recognizing that there is no way, statistically, to handle these subjects without possibly introducing bias, a tipping point analysis will be also be conducted. For comparison purposes, a completers analysis will also be performed. The following describes the method. A similar method will be applied to analyses for other objectives.

In general, Bayesian Multiple Imputation (MI) may be employed to impute the expected status at Month 60 for patients who have not completed follow-up and have not been identified as “terminal failures”. Terminal failures include any event which is counted as a CCS failure no matter what happens after such an event occurs such as a secondary surgical invention. The imputation algorithm uses a beta-binomial distribution to model the transition probabilities from the outcome at month  $j$  to that at month 60, separately for the treatment and control groups. Specifically, the probability of a success for a subject in treatment group  $t$ , with last follow-up  $j$  and last follow-up value  $r$  can be described using a beta distribution:

$$\Pi_{p,t,j,r} \sim \beta(1 + S_{p,t,j,r}, 1 + F_{p,t,j,r})$$

Where  $p$  = propensity score subclass = {1, 2, 3, 4, 5}

$t$  = treatment group = {coflex=S, Decompression=D}

$j$  = follow-up time = {3, 6, 12, 24, 36, 48}

$r$  = success or failure status at time  $j$  = {1=success, 0=failure}

$\Pi_{p,t,j,r}$  = Month 60 success probability for subjects in subclass  $p$ , in treatment group  $t$ , who were successes ( $r=1$ ) or failures ( $r=0$ ) at follow-up time  $j$ .

$S_{p,t,j,r}$  = Number of Month 60 successes for subjects in subclass  $p$ , in treatment group  $t$ , who were successes ( $r=1$ ) or failures ( $r=0$ ) at follow-up time  $j$ .

 Guidance for Industry and FDA Staff Clinical Data Presentations for Orthopedic Device Applications Document issued on: December 2, 2004.

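### Section 7.1 assigns IDE-based informative priors to every Objective, contradicting section 7.7.4, which rules them out for Objective 4; 7.6 and the synopsis name no prior for that test.

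*Combined protocol and SAP*

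**What the plan says.** Section 7.1, the general introduction to the statistical methods, says that "a Bayesian design with informative priors has been specified for each Objective. For these Objectives, patient-level data from the IDE study are used" to form the PAS priors. Objective 4 is not excepted.

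Section 7.7.4, on sample size for Objective 4, says: "Non-informative priors were assumed for the both comparisons groups, since IDE results cannot be used as the basis of an informative prior" when the comparison is with that same trial. The IDE result enters as known comparator data: "exactly 135 successes were observed among 204 evaluable patients in the coflex IDE analysis set". It continues: "A design was identified that uses a non-inferiority margin of -0.1175 and a 0.95 posterior probability threshold". The stated operating characteristics are type 1 error 0.045 and power of about 80%.

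Section 7.6, the analysis section for Objective 4, gives hypotheses and a decision rule ("Non-inferiority will be concluded if the posterior probability is at least equal to 0.95") but no prior. The synopsis entries for Objective 4 name none either.

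Section 7.11.1 sets out the multiple imputation for Month 60. Its step 4 puts the informative prior on the device group. Of the remaining objectives it says: "A similar method will be applied to analyses for other objectives".

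**The concern.** Objective 4 asks whether coflex performs as well in routine use as it did in the IDE trial. If the IDE data also form the prior for the PAS success rate, that rate is pulled towards the result it is being tested against. An analyst who took 7.1 at face value would be running a different test from the one whose error rates the plan quotes, and 7.6 would not correct the mistake. Passing Objective 4 also has a consequence: the PAS counts are then pooled with the IDE counts to update the posterior probabilities against fusion (7.6).

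**Working it through.** **Inputs**
- IDE coflex result: 135 of 204 = 0.6618, reported as 0.662 (7.7.2, 7.7.4).
- PAS coflex sample size: 150 (4.2).
- Margin 0.1175, posterior threshold 0.95 (7.7.4 and synopsis).
- Type 1 scenario: PAS rate 0.10 below IDE, about 0.562 (7.7.4).
- Boundary of the 0.1175 margin: 0.662 − 0.1175 = 0.5445.
- Informative Month 24 coflex prior: beta(135.5, 69.5), which 7.7.2 and 7.7.3 set for Objectives 2 and 3. Using it for Objective 4 is an assumption, since no informative prior for Objective 4 is given anywhere.

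**Formula**

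With x PAS successes and a beta(a, b) prior on the PAS rate:
- p_PAS | x ~ beta(a + x, b + 150 − x)
- p_IDE ~ beta(135.5, 69.5), that is, beta(0.5, 0.5) updated by 135 successes and 69 failures
- Pass if P(p_PAS > p_IDE − 0.1175) ≥ 0.95, by numerical integration over p_IDE

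The pass mark c is the smallest x that passes. The probability of passing at true rate p is the exact tail P(X ≥ c) for X ~ Binomial(150, p).

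**Step 1: reproduce 7.7.4 with a non-informative prior**

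With a = b = 0.5, the posterior probability is 0.945 at x = 94 and 0.959 at x = 95, so c = 95 (63.3%).
- Power at p = 0.6618: 0.795, against about 80% stated.
- Type 1 error at p = 0.6618 − 0.10 = 0.5618: 0.045, against 0.045 stated.
- Probability of passing at 0.5445: 0.017.

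With a = b = 1, the pass mark is also 95, so the choice between these two priors makes no difference here.

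**Step 2: follow 7.1 instead**

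With a = 135.5 and b = 69.5, and margin and threshold unchanged:
- With no PAS data, the posterior probability of non-inferiority is 0.994, already above 0.95.
- The posterior probability is 0.944 at x = 81 and 0.952 at x = 82, so c = 82 (54.7%).
- The prior carries 135.5 + 69.5 = 205 of 205 + 150 = 355 effective patients, or 58%.

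| True PAS rate | Non-informative (c = 95) | IDE prior (c = 82) |
|---|---|---|
| 0.5445 (0.1175 boundary) | 0.017 | 0.51 |
| 0.562 (plan's type 1 scenario) | 0.045 | 0.68 |
| 0.662 (power scenario) | 0.80 | 0.999 |

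**Step 3: sensitivity to a discounted prior**

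| Weight on IDE data | Posterior with no PAS data | Pass mark | Pass probability at 0.5445 | Pass probability at 0.562 |
|---|---|---|---|---|
| 80% | 0.991 | 85 | 0.32 | 0.49 |
| 50% | 0.978 | 89 | 0.13 | 0.24 |

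The size of the effect depends on the prior assumed, but even at half weight the threshold is met before any PAS outcome is seen.

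**The case against.** The strongest reply is that the specific text already settles the question. Section 7.7.4 addresses this exact point, gives the correct prior and gives the reason. Although it is a sample-size section, 7.7 is where this plan sets its priors: beta(82.1, 62.1) for Objective 1 in 7.7.1 and beta(135.5, 69.5) for Objective 2 in 7.7.2. Silence in 7.6 means little by itself, because 7.4 (Objective 2) names no prior either. The synopsis names an informative coflex prior for Objectives 1 to 3 and none for Objective 4, and its version of the 7.1 text omits the sentence about each Objective. All of this stands, and it establishes what was intended.

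Two further replies stand in part.
- Step 4 of 7.11.1 is weak evidence for an informative prior in Objective 4. It is written for Month 60 and a difference from decompression, so it cannot be applied literally to a Month 24 comparison with the IDE trial, and the plan promises only a similar method elsewhere.
- The 7.1 sentence might have had the later update against fusion in mind. It does not say so, and that update is not the non-inferiority test.

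A reader might infer that Objective 4 is designed to confirm itself, or that the quoted 0.045 is wrong. The documents support neither: 7.7.4 forbids the IDE prior, and 0.045 is correct for the scenario and design stated there.

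A reader might also say that a PAS population at the inferiority boundary would usually pass under 7.1. With the 0.1175 margin it would pass about half the time (0.51). A true rate of 0.562 lies inside that margin, so the 0.68 there is a departure from the plan's own type 1 scenario, not a false pass against the 0.1175 null. Higher figures, such as a pass mark of 80/150 and a probability of 0.79 at 0.562, come from combining the IDE prior with the fixed bound and 0.10 margin printed in 7.6. That margin conflicts with the 0.1175 in the synopsis and 7.7.4.

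What the objection does not remove is the unqualified statement in 7.1, which contradicts 7.7.4, and the absence of any prior in the section that defines the test.

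**Conclusion.** The contradiction is real and lies in the current text, but it is a drafting defect and not a flaw in the intended design. The intended prior for Objective 4 is non-informative, and the plan's stated type 1 error and power reproduce on that basis. The harm arises only if 7.1 is followed. On the assumptions of beta(135.5, 69.5) for the PAS rate, 150 patients, margin 0.1175 and threshold 0.95, the pass mark then drops by 13 successes (95 to 82), and the probability of passing at the boundary is about 30 times the intended value (0.51/0.017 = 30). Because the prior decides the outcome of a regulatory objective, it should be stated once, in the analysis section, before outcomes are unblinded.

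**What to change.** - Section 7.1: limit the sentence on informative priors to Objectives 1 to 3.
- Section 7.6 and the synopsis: state that the PAS coflex rate in Objective 4 has the non-informative prior used in the 7.7.4 simulations, with no contribution from IDE data. The prior should be named. Section 7.7.4 says only that it is non-informative; beta(0.5, 0.5) appears in 7.7.2 and beta(1, 1) is used for controls in 7.11.1. Both give the pass mark of 95/150.
- Section 7.11.1: state that, for Objective 4, step 4 uses that same prior.

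This changes wording only. Enrolment, data collection and the quoted operating characteristics are unaffected. The conflict between the 0.10 margin in 7.6 and the 0.1175 margin in the synopsis and 7.7.4 is a separate point that must also be reconciled.
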